mHealth-Assisted Conditional Cash Transfers to Improve Timeliness of Vaccinations (MINT)

ClinicalTrials.gov ID NCT03252288

Statistical analysis

For each participant, outcomes are observed at three time points (corresponding to timely vaccinations at 6, 10 and 14 weeks, respectively). The probability of timely vaccinations and its association with reminders and incentives will be analyzed in a bivariable analysis and using a random effects logistic regression model. The outcome variable is 1 if the vaccination was received on-time, and 0 if early, delayed, or not received at all. The primary covariates of interest are indicator variables for the receipt of reminders only (“*reminder*”) and the receipt of reminders with an incentive offer (“*reminder+incentive*”). For arm 1 the value of both covariates is 0 for all three time points. For outcomes in arm 2, the value for *reminder* (and for arm 3 the value for *reminder+incentive*) is 1 if the mHealth system confirmed delivery of the reminder, and 0 for all other observations. Additional covariates (e.g. mother’s education, rural vs. urban residence, recruitment from health facilities vs. the community) will control for differences in participant characteristics between study arms and their association with vaccination timeliness. Interactions of *reminder* and *reminder+incentive* with these covariates describe systematic variation in the effects of reminders and incentives on vaccination timeliness. Models will control for the number of phone-based contacts prior to or within the timeliness window for any given vaccination, and standard errors will be adjusted to account for clustering at the level of the health facility catchment area.

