Assignment to study arms is implemented at the level of the vaccination event, with all vaccination events scheduled during a phase assigned to the corresponding arm. T_1 , the beginning of Phase 1, denotes the time of participants' enrollment into the control arm. At time T_2 , the beginning of Phase 2, all participants are rolled over to the arm with reminders; at time T_3 , the beginning of Phase 3, all participants are rolled over to the arm with reminders combined with incentives. While T_2 and T_3 denote fixed points in calendar time, variation in delivery dates across participants results in between- and within-individual variation in the assignment of vaccination events across the three arms. **Table 2** shows all possible combinations of vaccination event assignments to study arms at the level of the participant. With dates of birth exogenously determining children's vaccination schedules, shifts in T_2 and T_3 directly affect the number of vaccination events that may be observed in each study phase. Based on the distributions of expected delivery and vaccination due dates, T_2 and T_3 are chosen such that the expected number of vaccination events is approximately equal across the three arms. With T_2 and T_3 being random in relation to mothers' delivery dates, and thus children's vaccination schedules, the assignment of vaccination events across arms may be considered quasi-random. Loss to follow-up and other reasons for non-delivery of vaccination reminders result in exposure indistinguishable from the control condition.

The assignment to study arms based on scheduled vaccination dates, and the simultaneous transition of all participants between study arms, address concerns that the individual randomization into, and co-existence of, incentive and non-incentive arms are not considered viable within closely-knit communities. While cluster randomization was considered as an alternative approach, the heterogeneity of clusters suggests that this approach would confound the effects of settings with the effects of reminders and incentives.

Study setting

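### The primary timeliness model names no visit term although the fixed phase order ties arm to visit; if timeliness differs by visit, the arm contrasts are biased by an amount and in a direction the documents do not settle

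*SAP*

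**What the plan says.** The SAP and the Protocol (Statistical analysis) describe the same model; the SAP adds a bivariable comparison: timeliness "will be analyzed in a bivariable analysis and using a random effects logistic regression model". Each child contributes three events: "For each participant, outcomes are observed at three time points (corresponding to timely vaccinations at 6, 10 and 14 weeks, respectively". Exposure is one indicator for reminders and one for reminders plus incentive. Each "is 1 if the mHealth system confirmed delivery of the reminder, and 0 for all other observations". The further covariates are given as examples (education, residence, recruitment route) and "will control for differences in participant characteristics between study arms and their association with vaccination timeliness". One event-level covariate is named: "Models will control for the number of phone-based contacts prior to or within the timeliness window for any given vaccination". Visit is not named.

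The Protocol (Assignment to study arms and transitions between arms) assigns each event to the phase in which it falls due. At T2 everyone moves to reminders, and at T3 "all participants are rolled over to the arm with reminders combined with incentives". The dates are set by total counts: "T_2 and T_3 are chosen such that the expected number of vaccination events is approximately equal across the three arms". No balance by visit is stated. The Protocol does note that "variation in delivery dates across participants results in between- and within-individual variation in the assignment of vaccination events across the three arms", so the link between arm and visit is a tendency, not a rule.

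**The concern.** A child can reach a later arm only at a later visit. Choosing T2 and T3 without regard to delivery dates supports comparing children at the same visit who were born at different times. It does not equalise the mix of 6, 10 and 14 week events across arms.

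The random intercept (read here as one per child) does not help. It gives weight to contrasts within a child, and there arm and visit only ever move forward together. If, say, 14-week vaccinations are less often timely than 6-week ones, whatever the arm, the model books some of that deficit as harm from incentives. If they are more often timely, it books it as benefit. Both contrasts with control are exposed, the incentive contrast most.

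**Working it through.** **From the documents.** Events due 6, 10 and 14 weeks after birth; one phase order; about equal totals per arm; within-child correlation 0.2; control timeliness 65%, one rate for all visits; target differences of 10 and 15 points (Protocol, Statistical power). The plan gives no figure for visit mix or timeliness by visit, so there is none to reproduce.

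**Assumed.** Births uniform over R weeks; T2 and T3 at the tertiles of due dates; every reminder delivered; no carry-forward of delays; no true effect; timeliness 70, 65 and 60% at the three visits; phone count not yet in the model. R is not stated, so 12, 16, 26 and 34 weeks are shown. The upper end is an indirect bound: if all women are enrolled by the end of Phase 1 and the third trimester is taken as 13 weeks, then R ≤ R/3 + 23, about 34.

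**Step 1, visit mix.** Count weeks from the first birth. For R ≥ 12, T2 = 10 + R/3 and T3 = 10 + 2R/3. The births whose 6, 10 and 14 week events fall before T2 span R/3 + 4, R/3 and R/3 - 4 weeks. These sum to R, one third of the 3R total. So in control:
- 6-week share = 1/3 + 4/R
- 10-week share = 1/3
- 14-week share = 1/3 - 4/R

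Arm 3 is the mirror image, and arm 2 has one third of each.

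**Step 2, bivariable comparison.** With a fall of d points per visit, the control mean is 65 + 8d/R and the arm 3 mean is 65 - 8d/R. The spurious difference is -16d/R for incentives and -8d/R for reminders. At R = 26 and d = 5: -16 × 5/26 = -3.1 and -8 × 5/26 = -1.5 points.

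**Step 3, model with a child effect.** Generalised least squares, b = (X'V⁻¹X)⁻¹X'V⁻¹μ, with X holding the intercept and two arm indicators, V compound-symmetric with correlation 0.2, and μ = 70, 65, 60. The last column is SE(with visit)/SE(without) for the incentive contrast.

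| R (weeks) | 6-week share, control vs arm 3 | Bivariable bias, reminders / incentives | Child-effect model bias, reminders / incentives | SE ratio |
|---|---|---|---|---|
| 12 | 67 vs 0% | -3.3 / -6.7 | -4.1 / -8.2 | 1.49 |
| 16 | 58 vs 8% | -2.5 / -5.0 | -3.4 / -6.8 | 1.23 |
| 26 | 49 vs 18% | -1.5 / -3.1 | -2.3 / -4.7 | 1.08 |
| 34 | 45 vs 22% | -1.2 / -2.4 | -1.8 / -3.7 | 1.05 |

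A random-intercept logistic fit (intercept SD 1.15) agrees within 0.1 point; its incentive figure at 26 weeks is -4.6. The child effect makes the bias larger than in the bivariable comparison. Every figure scales with the gradient: at 2 points per visit it is 40% as large, so the incentive bias is -3.3, -2.7, -1.9 and -1.5. A rise reverses the signs; a flat profile gives zero.

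**Step 4, false positives.** In a simulation at R = 26 (360 children, intercept SD 1.0, 5-point gradient in either direction, 300 runs each), the null incentive effect was rejected in 20 to 22% of runs without visit terms and 3 to 7% with them.

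**Step 5, phone count.** A count of earlier contacts rises with visit order within a child. It removes some or most of the bias, depending on R. The wording also admits the call made about the child's own current vaccination. Staff phone when no vaccination report has arrived (Protocol, Study activities), so that call can depend on the outcome. With assumed call rates of 35% if timely and 80% if not, and the own-visit call counted, the model gave spurious effects of about +11 to +19 points (reminders) and +21 to +25 (incentives) over these windows. Adding visit left them essentially unchanged.

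**The case against.** **The plan does not rule visit out.** True. The covariate list is open, and a reader might infer from its silence that visit is excluded; the text does not say that. But the list's stated purpose is participant characteristics, which visit is not, and the bivariable analysis states no adjustment. An analyst following the plan as written would have no visit term.

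**Nothing shows a gradient across these visits.** This also stands. The Protocol's background cites delays of 69% for a third DPT dose and 46% for a measles-containing vaccine. A reader might take these as a gradient and read off a direction, but they are not rates compared across the 6, 10 and 14 week visits. The schedule also shifts after a delay (Protocol, Scheduling system). If timeliness is scored against the shifted date, one reason for later visits to be later largely disappears. The 5-point step is an illustration only.

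**The remedy costs precision where it is needed most.** Correct. Adding visit lowers mean squared error for the incentive contrast only if the bias exceeds √(ratio² - 1) standard errors: √(1.49² - 1) = 1.10 at 12 weeks, but √(1.08² - 1) = 0.41 at 26. With a narrow window and a small gradient, the precision lost can exceed the bias removed. That is the price of arm and visit being nearly inseparable there.

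**The phone count already adjusts for this.** Only in part, and only if it excludes the current visit's follow-up call.

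**Conclusion.** The point holds as a gap in the specification that is cheap to close. The missing visit term and the arm-visit link follow from the documents alone. The size does not: it rests on the assumed birth spread, gradient, full delivery and unshifted schedule. Under the 5-point illustration the spurious incentive effect runs from about -8 points (12-week window) to about -3.7 (34 weeks) before the phone count, against planned effects of 10 and 15.

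Two stronger readings should be resisted. A reader might infer that the trial will understate, or overstate, the benefit of incentives; the documents fix neither sign nor size, and flat timeliness means no bias. A reader might also infer that a visit term makes the contrasts unbiased. It brought the illustrated bias to about zero because the assumed visit effect was exactly what the term models. It does not remove calendar-time effects, which the Protocol's Discussion concedes, or carry-forward of delays, or bias from outcome-dependent phone contacts. Confidence is medium.

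**What to change.** - Pre-specify scheduled visit (6, 10, 14 weeks) as a categorical fixed effect in the primary random-effects logistic model.
- Stratify the bivariable comparison by visit.
- Tabulate events by visit and arm, so that readers can see how far the two overlap.
- Flag separately that the phone-contact count may depend on the outcome, and state which contacts it includes.
- Keep calendar time and carry-forward of delays as stated limitations.

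The cost is two parameters and no new data. At within-child correlation 0.2 and before the phone count, the incentive standard error rises by about 49% (12-week window), 23% (16), 8% (26) and 5% (34). This is not converted to power. The listed inputs, read literally, give 360/(1.18 × 1.4) = 217.9 effective events per arm and power of about 62.5% and 94.2%, not the stated 72% and 98%, so there is no firm base to scale from.

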For each participant, outcomes are observed at three time points (corresponding to timely vaccinations at 6, 10 and 14 weeks, respectively). The probability of timely vaccinations and its association with reminders and incentives will be analyzed using a random effects logistic regression model. The outcome variable is 1 if the vaccination was received on-time, and 0 if early, delayed, or not received at all. The primary covariates of interest are indicator variables for the receipt of reminders only (“*reminder*”) and the receipt of reminders with an incentive offer (“*reminder+incentive*”). For arm 1 the value of both covariates is 0 for all three time points. For outcomes in arm 2, the value for *reminder* (and for arm 3 the value for *reminder+incentive*) is 1 if the mHealth system confirmed delivery of the reminder, and 0 for all other observations. Additional covariates (e.g. mother’s education, rural vs. urban residence, recruitment from health facilities vs. the community) will control for differences in participant characteristics between study arms and their association with vaccination timeliness. Interactions of *reminder* and *reminder+incentive* with these covariates describe systematic variation in the effects of reminders and incentives on vaccination timeliness. Models will control for the number of phone-based contacts prior to or within the timeliness window for any given vaccination, and standard errors will be adjusted to account for clustering at the level of the health facility catchment area.

Statistical power

Across 400 participants we expect up to 1,200 data points on vaccination timeliness. Assuming (a) that these data points are distributed equally across the 3 study arms (standard of care; reminders only; reminders and incentive); (b) a 10% attrition rate; (c) equal cluster sizes of 10 women per health facility catchment area, with an intra-cluster correlation of 0.02; (d) 3 observations per child, with a within-child correlation of 0.2; (e) a baseline rate of vaccination timeliness of 65% in the control condition; and (f) a 10 (15) percentage point difference associated with reminders (reminders and incentives), the power ($\alpha=.05$, 2-tailed) to detect such difference is 72% (98%).

Dissemination

Results will be shared with stakeholders at the regional and national levels, presented at national and international conferences, and published in high impact academic journals.

Data sharing

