Efforts will be made to develop a data repository for the storage of de-identified study data. Investigators wishing to use study data to answer new research questions may submit data analysis concept proposals for consideration by the Principal Investigators. The Principal Investigators will review the proposal and will provide those submitting scientifically rigorous and promising proposals access to the data repository to address their research questions.

Discussion

This study examines the efficacy of mobile phone-based reminders and incentives in the form of conditional financial transfers for offsetting demand-side barriers to timely childhood vaccinations in Tanzania. Our implementation strategy has several unique components, including the use of a USSD-based birth and vaccination event notification system, an adaptive schedule for vaccination reminders which is derived from the date of the preceding event, a tiered incentive system, and the automated disbursement of mobile phone credit for eligible timely vaccinations.

The study is subject to several limitations: First, feasibility considerations limit the study area to include only health facilities and their catchment areas within approximately 30 km of Mtwara municipality. More remote populations may face additional barriers that cannot be evaluated in this study. Second, only women with access to mobile phones are included in the study. To minimize selection bias, women could designate anyone with a mobile phone to be their study contact. However, for women relying on such authorized agents, receipt of messages and payments for timely vaccinations could remain a challenge. Third, reminder schedules and payments for timely vaccinations are based on client-reported birth and vaccination dates. The dependence on client reports may introduce delays, affect schedule accuracy, and motivate inaccurate reporting of vaccination dates. Comprehensive quality control, including automated alerts to study staff for participant follow-up, algorithms that identify inconsistencies in near real time, and an in-person end-line survey with a review of government-issued vaccination cards, will be used to assess and/or mitigate these concerns. Fourth, it is plausible that follow-up phone calls by study staff to ascertain birth outcomes, the timing of past vaccinations, and/or the

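### The only specified model codes exposure by confirmed message delivery, not by assigned phase, so it is an as-treated contrast; no analysis by assigned phase is stated.

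*SAP*

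**What the plan says.** - **Assignment.** The Protocol (Assignment to study arms and transitions between arms) works at the level of the vaccination event, with "all vaccination events scheduled during a phase assigned to the corresponding arm". Because birth dates drive the schedules, it argues that "the assignment of vaccination events across arms may be considered quasi-random".
- **Exposure in the model.** In the SAP, and identically in the Protocol's Statistical analysis section, the covariate *reminder* (arm 2) or *reminder+incentive* (arm 3) "is 1 if the mHealth system confirmed delivery of the reminder, and 0 for all other observations".
- **Reason given.** The Protocol's assignment section states: "Loss to follow-up and other reasons for non-delivery of vaccination reminders result in exposure indistinguishable from the control condition".
- **Analyses named.** The SAP says that timeliness "will be analyzed in a bivariable analysis and using a random effects logistic regression model". It does not say what defines the groups in the bivariable part.
- **Adjustment.** Example covariates are education, residence and recruitment route. In addition, "Models will control for the number of phone-based contacts prior to or within the timeliness window for any given vaccination".
- **Messages.** The Protocol describes two messages before the due date (Mobile phone reminder system). It adds a third, two weeks after the due date, only when no vaccination has been confirmed (Study activities). Neither document says which of these counts as the reminder whose delivery must be confirmed.

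**The concern.** The design's argument for comparability attaches to the scheduled phase. The model compares a different pair of groups: events whose message got through, against arm 1 plus every arm 2 or arm 3 event whose message did not. Whether a message is confirmed as delivered is settled after assignment, and may depend on the phone, the network or the woman's circumstances.

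The stated reason concerns what an unreached woman received. It does not show that unreached women would have vaccinated on time as often as reached women. If they would not, the coefficients mix the effect of the messages with that difference.

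The planned adjustment may remove part of this but cannot be relied on to remove all of it. None of the named covariates measures how reachable a woman is by phone, although the baseline survey records phone ownership and use. The contact count arises after assignment, and staff phone when no vaccination report arrives, so it may itself be linked to the outcome.

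The undefined reminder adds a second problem. If the message sent two weeks after the due date counts, exposure depends on the child not yet being confirmed as vaccinated.

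**Working it through.** **1. The groups compared**

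| | By assignment | By the model's coding |
|---|---|---|
| Reference | arm 1 | arm 1 + undelivered arm 2 + undelivered arm 3 |
| *reminder* | all arm 2 | delivered arm 2 |
| *reminder+incentive* | all arm 3 | delivered arm 3 |

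**2. Crude bias with no true effect (illustration)**

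From the Protocol's Statistical power section: 65% timeliness and equal arms. Assumed: nd, the share of arm 2 and arm 3 events undelivered, and gap, delivered minus undelivered timeliness.

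- Delivered: p_d = 0.65 + nd × gap. Undelivered: p_u = p_d − gap.
- Reference: (0.65 + 2 × nd × p_u) / (1 + 2 × nd).
- Bias = p_d − reference = 3 × nd × gap / (1 + 2 × nd).
- Undelivered share of the reference group = 2 × nd / (1 + 2 × nd).

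At nd = 0.10 and gap = 0.10, p_d = 0.66, p_u = 0.56 and the reference is (0.65 + 0.20 × 0.56) / 1.20 = 0.635. The bias is 0.025.

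| nd | gap | Bias (points) | Undelivered share of reference |
|---|---|---|---|
| any | 0 | 0 | – |
| 5% | 5 points | +0.7 | 9% |
| 10% | 5 points | +1.3 | 17% |
| 10% | 10 points | +2.5 | 17% |

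A gap of opposite sign gives the same bias with opposite sign. Grouping by assigned phase gives zero in every row, before any calendar-time effect. These are unadjusted figures.

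**3. The plan's power, and dilution under assigned-arm coding**

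Events per arm: 1,200 × 0.9 / 3 = 360. Design effects: within child 1 + 2 × 0.2 = 1.4; cluster 1 + 9 × 0.02 = 1.18; product 1.652. The method is a two-sided 5% normal approximation for two proportions, with pooled variance under the null and n = 360 / design effect.

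The plan states 72% (98%) for 10 (15) points. All stated inputs give 62.5% (94.2%); the within-child effect alone gives 69.8% (97.0%). The plan's figure is not reproduced with all its inputs. That is a separate matter, since its method is not stated, and only the fall is used here.

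If only delivered messages work, the effect by assigned arm is (1 − nd) times the planned effect.

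| Non-delivery | Effects (points) | Power, reminder | Power, reminder+incentive |
|---|---|---|---|
| 0% | 10 / 15 | 63–70% | 94–97% |
| 10% | 9 / 13.5 | 53–60% | 88–93% |
| 20% | 8 / 12 | 44–50% | 79–85% |

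With n set to match the stated 72% (271 effective events per arm), the sequence is 72% (98%), 62% (94%), 52% (87%).

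**4. Which schedule defines the phase**

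A late dose moves the remaining due dates (Protocol, Scheduling system and Study activities), so late vaccinators drift into later phases. This was simulated with no true effect and full delivery. Assumptions: births uniform over 90 or 120 days; T2 and T3 at the thirds of birth-based due dates; participant intercept SD 1.0; on-time delay exponential with mean 7 days, capped at 28; late delay 28 days plus exponential with mean 21.

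- Crude timeliness by updated phase: about 66%, 67% and 63% in arms 1, 2 and 3. Arm 3 minus arm 1 is about −3 points, all spurious.
- Crude timeliness by birth-based phase: about 65% in each arm.
- Random-intercept model by updated phase: odds ratios 0.99–1.02, close to null.
- Share of events by updated phase: about 26%, 25% and 49%, so arms 1 and 2 hold roughly 255–290 events each, not 360.
- Six-week events falling in Phase 3: about 2–10%, or 8–36 of 360.

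**The case against.** **The coding is disclosed and deliberate.** The study aim speaks of efficacy, the covariates are named as receipt, and a reason is given. That stands: this is a prespecified effect-of-receipt analysis, not a slip. But naming the estimand does not make delivered and undelivered events comparable, and no companion analysis by assigned phase would show a problem.

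**Covariates may deal with it.** They are introduced as examples, so phone access is not excluded, and rural residence and education are already named. Network faults, which the Protocol expects, may be unrelated to timeliness. This stands as a reason why the bias could be small or absent. It does not establish that it is.

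**Stronger readings the documents do not support.**
- A reader might take "a 10% attrition rate" as a rate of non-delivery. It is a power assumption about lost data. Outcomes can come from vaccination cards at the end-line survey, so a failed message and a missing outcome are different things, and an event with no outcome cannot enter the reference group.
- A reader might infer that the bias favours the interventions, because the Introduction says that rural, remote and poorer households are less fully vaccinated. That concerns coverage across low- and middle-income countries, not timeliness by message delivery among women selected for phone access.
- The Protocol's Discussion does say that "for women relying on such authorized agents, receipt of messages and payments for timely vaccinations could remain a challenge". This makes selective receipt plausible, but delivery to an agent's phone may still be confirmed. It gives neither a rate nor a direction.

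**Grouping by assigned arm is not free of bias everywhere.** This also stands. A crude comparison by updated phase would bring in the −3 points shown above, so the bivariable analysis needs its own rule.

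**Conclusion.** The concern holds as a point about exposure coding. The primary coefficients are an as-treated contrast that does not inherit the design's claim of quasi-randomness, and nothing in the plan states an analysis that does. The size and sign of any bias are unknown. The 0 to 2.5 points shown are unadjusted illustrations resting on assumed delivery rates and gaps, against a planned reminder effect of 10 points. The documents do not support saying that the trial will overstate its effects. Calendar-time confounding, which the Protocol's Discussion acknowledges, remains under either coding.

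**What to change.** **Primary model (SAP; Protocol, Statistical analysis).** State that *reminder* = 1 for every event assigned to arm 2 and *reminder+incentive* = 1 for every event assigned to arm 3, whether or not delivery was confirmed. In the Protocol's assignment section, state that undelivered events stay in their assigned arm for this analysis.

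**Secondary model.** Keep the delivery-coded model, labelled as-treated. Count only messages sent before the due date as the reminder. Adjust for baseline phone ownership and use and for reliance on an authorized agent.

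**Bivariable analysis.** Group by phase fixed from birth-based due dates. If updated phase is used instead, state that late vaccinators are concentrated in arm 3.

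**Sensitivity analyses.** Refit the model with birth-based phases. Use six-week events alone for the reminder contrast only, since too few fall in Phase 3 to inform the incentive contrast. Birth-based phase should not replace the primary coding: under the assumed delays it misplaces about 20% of events.

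**Cost.** A few sentences and no new data. The price is the dilution shown in the working, which assumes 360 events per arm. Under the assumed delays, arms 1 and 2 would hold fewer on the updated schedule, with either coding.
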